6.1.2. HANDLING OF MISSING TRANSFUSION ASSESSMENTS

In order to be considered transfusion independent, a subject must have completed continuous transfusion assessments throughout the qualifying observation period where his/her transfusion independence is determined. An apparent transfusion free period with one or more missing transfusion assessments will not be considered a qualifying 8-week or 24-week TI period. Subjects with no qualifying observation periods will be considered non-responders. In addition, the number (%) of patients who have missed one or more visits will be tabulated.

6.1.3. ANALYSIS METHODS

Number and percent of subjects achieving TI and the corresponding 2-sided 80% confidence

interval (CI) will be summarized.

6.2. MAJOR SECONDARY ENDPOINTS

6.2.1. DEFINITION

24-Week RBC TI Rate

24-week RBC TI rate is defined as the proportion of subjects without any RBC transfusion during any consecutive 24 weeks (168 days) starting from Study Day 1 until the end of study. The starting date of 24-week RBC TI must be between Study Day 1 and End of treatment Phase ending date (date of last dose of study medication + 30 days).

Time to 8-Week (24-Week) RBC TI

Pertaining only to subjects who achieved TI, time to the 8-week (24-week) RBC TI is defined as the interval from Study Day 1 to the first day of the first 8-week (24-week) RBC TI period.

Duration of RBC TI

Pertaining only to subjects who achieved TI for at least 8 weeks, duration of RBC TI is defined as the maximal number of consecutive transfusion-free days that are ≥ 56 days (8 weeks). For subjects maintaining transfusion-free by the time of the cutoff date for the analysis or who withdraw from the study, duration will be censored at the date of the last transfusion evaluation. Duration of 24-week TI is defined similarly.

Rate of Hematologic Improvement per International Working Group Response Criteria 2006 (IWG 2006)

The IWG criteria for HI define specific responses of cytopenias in the three hematopoietic lineages: erythroid (HI-E), platelet (HI-P), and neutrophil (HI-N). Rate of hematologic improvement of erythroid lineage is the focus of this study, which is defined as the proportion of subjects who achieve HI-E.

HI-E is defined as a hemoglobin (Hb) rise of at least 1.5 g/dL above pretreatment and lasting at least 8 weeks or reduction of at least 4 units of RBC transfusions/8 weeks compared with the prior RBC transfusion burden. Pretreatment Hb level is defined as the average of all the Hb values in the 8 weeks prior to study entry, including the value on Cycle 1 Day 1 and excluding values that were within 14 days after transfusion (thus considered to be influenced by transfusion). If there were no Hb values that met this definition of not being influenced by transfusions, then the baseline value is used.

Rate of Complete Remission (CR) or Partial Remission (PR)

Defined as the proportion of subjects who achieve CR, or PR per IWG 2006 [4].

Overall Survival (OS)

OS is defined as the interval from Study Day 1 to death from any cause. Survival time of living subjects will be censored on the last date a subject is known to be alive or lost to follow-up.

Time to Progression to AML

Time to progression to AML is defined as the interval from Study Day 1 to the date of AML progression (bone marrow or peripheral blood blasts $\geq 20\%$). Subjects who have not progressed to AML at the cutoff date for the analysis or who withdraw from the study will be censored at the date of the last disease evaluation.

Amount and Relative Change in RBC Transfusions

Amount of RBC transfusions is defined as the total number of RBC transfusion units in a given post-baseline 8-week (any consecutive 56 days period) interval during study. The starting date of a post-baseline 8-week interval must be between Study Day 1 and End of treatment Phase ending date (date of last dose of study medication + 30 days). Relative change in RBC transfusions is defined as:

$$\text{Relative change in RBC Transfusion} = \frac{\text{amount of RBC transfusions} - \text{prior RBC transfusion burden}}{\text{prior RBC transfusion burden}} * 100 \%$$

Note that prior RBC transfusion burden is the maximum number of RBC units transfused over an 8-week period during the 16 weeks prior to Study Entry.

The best RBC transfusion reduction is defined as the “best” or the “minimum” number of RBC transfusions in any post-baseline 8-week interval. The time to the best transfusion reduction in an 8-week interval (in weeks), the minimum number of RBC transfusions received during this interval, and the relative change from baseline will be summarized.

Rate and Duration of Myeloid Growth Factor Usage

Rate of myeloid growth factor usage is defined as the proportion of subjects receiving any myeloid growth factors starting from Study Day 1; duration of myeloid growth factor administered starting from Study Day 1.

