10.2. Discontinuation of Study Treatment/Withdrawal from the Study

If a subject's study drug must be discontinued, this will not result in automatic withdrawal of the subject from the study.

Discontinuation of Study Treatment

A subject's study treatment must be discontinued if:

- The investigator believes that for safety reasons (eg, adverse event) it is in the best interest of the subject to discontinue study treatment
- The subject becomes pregnant
- The subject experiences disease progression or relapse
- The subject refuses further treatment
- A serious protocol violation has occurred, as determined by the principal investigator or the sponsor

End-of-treatment and posttreatment follow-up assessments should be obtained. The reason(s) a subject discontinues treatment will be recorded on the eCRF.

Withdrawal From the Study

A subject will be withdrawn from the study for any of the following reasons:

- Lost to follow-up
- Withdrawal of consent
- The sponsor discontinues the study

If a subject is lost to follow-up, every reasonable effort must be made by the study-site personnel to contact the subject and determine the reason for discontinuation/withdrawal. The measures taken to follow-up must be documented.

When a subject withdraws before completing the study, the reason for withdrawal is to be documented in the eCRF and in the source document. Study drug assigned to the withdrawn subject may not be assigned to another subject. Subjects who withdraw will not be replaced. If a subject withdraws from the study before the end of the Treatment Phase, end-of-treatment and posttreatment follow-up assessments should be obtained, unless the subject withdraws consent.

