6.2.2. ANALYSIS METHODS

Rate of 24-week TI, CR, PR, and hematologic improvement (HI), and other binary endpoints, will be summarized with percentage along with its 95% 2-sided exact Clopper-Pearson confidence interval.

The time to 8-week RBC TI and time to 24-week RBC TI will be summarized descriptively.

The Kaplan-Meier method will be used to estimate the distribution of duration of RBC TI for 8-week and 24-week TI responders, respectively. The distribution of OS and time to progression to AML will be summarized using similar Kaplan-Meier methods.

Amount and relative change in RBC transfusions will be summarized descriptively by time point.

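### The censoring rule for duration of RBC transfusion independence does not require the measured run to be ongoing, so read literally it can turn an observed end of response into a later censoring

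*SAP*

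**What the plan says.** SAP 6.2.1, among responders: "duration of RBC TI is defined as the maximal number of consecutive transfusion-free days", with a floor of 56 days. The next sentence sets the censoring: "For subjects maintaining transfusion-free by the time of the cutoff date for the analysis or who withdraw from the study, duration will be censored". The date is fixed too: "duration will be censored at the date of the last transfusion evaluation". Duration of 24-week TI is defined in the same way, so it inherits the rule.

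SAP 6.2.2 gives the estimator: "The Kaplan-Meier method will be used to estimate the distribution of duration of RBC TI for 8-week and 24-week TI responders". Protocol 11.3 also specifies Kaplan-Meier and adds nothing about events or censoring.

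Two further places matter. On stopping study drug, Protocol 10.2 says "this will not result in automatic withdrawal of the subject from the study"; withdrawal there means loss to follow-up, withdrawn consent, or the sponsor discontinuing the study. Protocol 9.2.1 has transfusions recorded every 4 to 6 weeks after treatment.

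**The concern.** The quantity measured belongs to a run, but the censoring is assigned by the status of the subject. The two agree for a responder with one run that is still open when observation stops. They part in two situations.

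- **Ended run, later withdrawal.** Suppose the longest run ends with a transfusion on day 120 and the subject withdraws on day 250. The duration is fully observed, yet the withdrawal part calls for censoring at the last transfusion evaluation, after the run is over.
- **Ended longest run, shorter spell at cutoff.** Suppose a 100-day run is complete and the subject is 30 days into a new transfusion-free spell at cutoff. The cutoff part can be read as covering this subject.

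The first route is realistic. A responder can relapse, stop drug, remain in follow-up with transfusions recorded, and withdraw later. Because sponsor discontinuation counts as withdrawal, early termination could on the literal reading censor every responder still in follow-up, including those already transfused again.

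Duration of TI is a named secondary endpoint. SAP 3.4 gives secondary endpoints more weight if 6 or 7 subjects reach TI, so an inflated durability estimate could matter in that zone.

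**Working it through.** The documents state no TI-duration median, event count or withdrawal rate, so there is no figure of the plan's own to reproduce. The check has three parts.

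**1. The text.** A duration in consecutive transfusion-free days stops at the next transfusion. A censoring time later than that transfusion counts days that were not transfusion-free. For an ended run the two sentences of SAP 6.2.1 therefore cannot both be followed.

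**2. Direction, on a small invented example.** Nine responders have durations in weeks of 9, 12, 16, 20, 26, 30, 34+, 40, 52+ (+ means censored). At each event the Kaplan-Meier estimate S is multiplied by (1 − 1/number at risk); the median is the first time at which S ≤ 0.5.

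- Run-level censoring: S = 8/9, 7/9, 6/9, 5/9, then 4/9 = 0.444 at week 26. Median 26.
- Week-12 relapse recoded as censored: 8/9 × 6/7 × 5/6 × 4/5 = 0.508 at week 26, then × 3/4 = 0.381 at week 30. Median 30.
- Week-12 and week-20 relapses recoded, flag only: 8/9 × 6/7 × 4/5 = 0.610 at week 26, then × 3/4 = 0.457 at week 30. Median 30.
- The same two, with time also carried on 16 weeks (to 28+ and 36+): 8/9 × 7/8 × 6/7 × 4/5 = 0.533 at week 30, then × 1/2 = 0.267 at week 40. Median 40.

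Turning an event into a censoring at the same or a later time can only raise the curve or leave it unchanged.

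**3. Size, by simulation.** All inputs are assumptions: TI starts uniformly on days 1–100; duration is 56 days plus an exponential with mean 120 days; data end uniformly between days 365 and 730; the stated share withdraws at a uniform time between reaching 56 days and data end. True median = 56 + 120 × ln 2 = 139 days.

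| Share withdrawing | Run-level rule | Literal, flag only | Literal, time carried to last evaluation |
|---|---|---|---|
| 0% | 139 | 139 | 139 |
| 10% | 139 | 147 | 151 |
| 20% | 139 | 158 | 168 |
| 30% | 139 | 170 | 192 |

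At 20% the excess is 19/139 = 14% (flag only) or 29/139 = 21% (time carried).

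A second simulation borrowed the 33-to-41-week lenalidomide response duration in Protocol 1 as the true median, again only as an assumption. At 20% yearly withdrawal, a run-level median of about 33 weeks becomes 38.3 (flag only) or 41.3 (time carried), and about 41 becomes 47.6 or 50.5. With no withdrawal, but 10% of relapsed responders in a shorter spell at cutoff, 32.7 weeks becomes 35.6 or 36.9.

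**Scale in this trial.** At the 30% target, 30 subjects give 30 × 0.30 = 9 responders. Under the first set of assumptions about 7.3% of responders are affected at 10% withdrawal and 14.6% at 20%, so 9 × 0.073 = 0.65 and 9 × 0.146 = 1.3 are expected. The chance that none is affected is (1 − 0.073)^9 ≈ 0.51 and (1 − 0.146)^9 ≈ 0.24.

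**The case against.** The best defence is that the sentence is loose template wording. Since duration is defined in consecutive transfusion-free days, a sensible programmer would censor only runs still open at cutoff or withdrawal. The AML rule in the same section supports this, because it uses the same shorthand: "Subjects who have not progressed to AML at the cutoff date for the analysis or who withdraw from the study will be censored". There it can only sensibly mean withdrawal without the event. That charitable reading is available, and nothing suggests a deliberate choice to censor observed relapses. But neither document states it, while the overall survival rule in the same section does restrict censoring to living subjects. The text still needs the condition.

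Three stronger readings are tempting and are not supported.

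- A reader might infer that the whole rule is wrong. For a responder with one run, being transfusion-free at cutoff means that the run is open, and censoring is correct.
- A reader might infer that the reported median will be overstated. That needs the literal reading and at least one affected responder early enough to move the median. Withdrawal is a narrow category that excludes stopping drug, and no rate is given.
- A reader might see an error in time to TI using the first run ("time to the 8-week (24-week) RBC TI is defined as the interval from Study Day 1 to the first day of the first 8-week") while duration uses the longest. These are different, legitimate summaries, and the censoring can be cured without changing either.

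The unstated handling of death while transfusion-free is missing detail, not a demonstrated bias.

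**Conclusion.** The point holds as a defect of specification. SAP 6.2.1 names no event for duration of TI and, read literally, censors responders whose measured run had already ended, which conflicts with its own definition of duration. The direction of any bias is certain (upward or none). Its size is not fixed by the documents: zero if nobody is affected, and in the first simulation about 8 to 31 days on a 139-day median at 10–30% withdrawal if only the flag changes, or 12 to 53 days if time is also carried forward. Those figures rest on assumed withdrawal rates and an assumed duration distribution. With about nine responders, the most likely number affected is none or one or two. The endpoint is secondary and descriptive; the primary decision rule counts TI responders and is untouched.

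**What to change.** Keep the longest run as the measured run and replace the censoring sentence in SAP 6.2.1 with: *The event is the first RBC transfusion after the start of the measured run; duration is censored at the last transfusion evaluation only if that run is still ongoing at the cutoff, at withdrawal or loss to follow-up, or at death.* Apply the same text to 24-week TI. Add the matching condition to the AML rule, so that withdrawal censors only subjects with no earlier progression to AML.

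The cost is a short SAP edit and one run-level derivation flag, with no new data. Reported durability may look slightly less favourable than under the literal rule.

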4.1. Inclusion Criteria

Each potential subject must satisfy all of the following criteria to be enrolled in the study:

1. 18 years of age
2. MDS according to World Health Organization (WHO, [Attachment 1](#)) criteria confirmed by bone marrow aspirate and biopsy within 12 weeks prior to first dose. A local laboratory report from this diagnostic bone marrow aspirate and biopsy must be approved by the sponsor.
3. IPSS low risk or intermediate-1 risk MDS ([Attachment 2](#))

-
4. RBC transfusion dependent
 - Received at least 4 units of RBCs over any 8 consecutive weeks during the 16 weeks prior to randomization
 - Pretransfusion Hb must have been ≤ 9.0 g/dLSource documentation for transfusions verified by the sponsor.
 5. Relapsed/refractory to ESA treatment; the sponsor must verify this diagnosis as defined by meeting any of the criteria below:
 - Received at least 8 weeks of treatment with a minimum weekly dose of epoetin alfa 40,000 U, epoetin beta 30,000 U or darbepoetin alfa 150 mcg (or equivalent agent/dose) without having achieved a Hb rise ≥ 1.5 g/dL or decreased RBC transfusion requirement by at least 4 units over 8 weeks
 - Transfusion dependence or reduction in Hb by ≥ 1.5 g/dL after hematologic improvement, in the absence of another explanation
 - Endogenous serum EPO level > 500 mU/mLSource documentation for failure of ESA treatment verified by the sponsor
 6. Adequate iron stores, defined as transferrin saturation greater than 20% and serum ferritin greater than 400 ng/mL, measured within the screening period, or adequate iron stores as demonstrated by recent (within 12 weeks prior to first dose) bone marrow examination with iron stain.
 7. ECOG performance status 0, 1 or 2 ([Attachment 3](#))
 8. Hematology laboratory test values within the following limits:
 - ANC $\geq 1.0 \times 10^9/L$ (ie, $\geq 1,000/mm^3$) independent of growth factor support. For the screening ANC to be considered growth factor independent, a 7-day period after stopping the growth factor should be observed, or 7 half-lives of growth factor used, whichever is longer.
 - Platelets $\geq 50 \times 10^9/L$ independent of platelet transfusion support. For the screening platelets to be considered independent of platelet transfusion support, platelet count must be stable for 3-4 days after the transfusion.
 9. Criterion numbering modified per Amendment 2
 - 9.1 Biochemical laboratory test values must be within the following limits:

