9.2.2. Hemoglobin Assessment

Hemoglobin levels will be measured weekly during the first 8 weeks, at the start of each cycle, and as clinically needed.

For a given subject, the same local laboratory should be used for each hematology assessment throughout the study, to the extent possible. Hematologic improvement-erythroid response (HI-E) is defined as a Hb rise of at least 1.5 g/dL above baseline, measured 28 days or more following the last RBC transfusion or reduction of at least 4 units of RBC transfusions/8 weeks compared with the 8 weeks prior to start of treatment (criterion adapted from IWG 2006).

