* Dysplastic changes should consider the normal range of dysplastic changes (modification).

† Modification to IWG response criteria.

‡ In some circumstances, protocol therapy may require the initiation of further treatment (eg, consolidation, maintenance) before the 4-week period. Such patients can be included in the response category into which they fit at the time the therapy is started. Transient cytopenias during repeated chemotherapy courses should not be considered as interrupting durability of response, as long as they recover to the improved counts of the previous course.

Proposed modified International Working Group response criteria for hematologic improvement

Hematologic Improvement*	Response criteria (responses must last ≥ 8 weeks)†
Erythroid response (pretreatment, < 11 g/dL)	Hb increase by ≥ 1.5 g/dL Relevant reduction of units of RBC transfusions by an absolute number of at least 4 RBC transfusions/8 weeks compared with the pretreatment transfusion number in the previous 8 weeks. Only RBC transfusions given for a Hb of ≤ 9 g/dL pretreatment will count in the RBC transfusion response evaluation†
Platelet response (pretreatment, $< 100 \times 10^9/L$)	Absolute increase of $\geq 30 \times 10^9/L$ for patients starting with $> 20 \times 10^9/L$ platelets Increase from $< 20 \times 10^9/L$ to $> 20 \times 10^9/L$ and by at least 100%†
Neutrophil response (pretreatment, $< 1 \times 10^9/L$)	At least 100% increase and an absolute increase $> 0.5 \times 10^9/L$ †
Progression or relapse after HI‡	At least 1 of the following: At least 50% decrement from maximum response levels in granulocytes or platelets Reduction in Hb by ≥ 1.5 g/dL Transfusion dependence

* Pretreatment counts averages of at least 2 measurements (not influenced by transfusions) ≥ 1 week apart (modification).

† Modification to IWG response criteria.

‡ In the absence of another explanation such as acute infection, repeated courses of chemotherapy (modification), gastrointestinal bleeding, hemolysis, and so forth. It is recommended that 2 kinds of erythroid and platelet responses be reported overall as well as by the individual response pattern.

Notes: Deletions to the IWG response criteria are not shown. To convert hemoglobin levels (concentrations) from grams per deciliter to grams per liter, multiply grams per deciliter by 10.

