3.6. CHANGE IN STUDY CONDUCT

Enrollment to the talacotuzumab arm was closed based upon the occurrence of a Grade 4 infusion-related reaction in the first subject who received talacotuzumab. All analyses and summaries described in this document will include data only in subjects who received daratumumab. Data listings will be provided separately for the single subject who received talacotuzumab.

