5. SUBJECT INFORMATION

5.1. DEMOGRAPHICS AND BASELINE CHARACTERISTICS

All demographic and baseline characteristic variables will be summarized for the ITT analysis set.

The stratification factors used during randomization (prior RBC transfusion burden) will be tabulated.

Two panels of baseline clinical laboratory tests specified will be summarized: hematology and serum chemistry. Frequencies of National Cancer Institute (NCI) Common Terminology Criteria for Adverse Events (CTCAE) grade at baseline will be reported.

Disease characteristics to be summarized will include WHO classification, IPSS risk category (low, intermediate-1), prior ESA treatment (Yes, No), serum EPO level (≤ 500 mU/mL, > 500 mU/ml), and time since initial diagnosis (months).

Hepatitis serology tests at baseline will be summarized by test type and results.

Transfusion history summaries will include total transfusion units, and prior RBC transfusion burden (4, >4 units). Prior RBC transfusion burden is defined as the maximum number of RBC units transfused over an 8-week period during the 16 weeks prior to Study Entry.

Medical history will be summarized including abnormality in physical examination.

In addition, summaries of bone marrow findings at baseline will be provided.

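### SAP 6.2.1 scores the transfusion route of HI-E against the worst 8 of the prior 16 weeks, while protocol 9.2.2 uses the 8 weeks before treatment; the change is not declared and, other rules fixed, can essentially only add responders by that route

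*SAP*

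**What the plan says.** SAP 6.2.1 lists HI under a heading that cites IWG 2006 and makes the erythroid lineage its focus. HI-E can be met by a hemoglobin rise or by a transfusion reduction. The second route requires a "reduction of at least 4 units of RBC transfusions/8 weeks compared with the prior RBC transfusion burden".

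The SAP defines the comparator twice. Later in 6.2.1: "prior RBC transfusion burden is the maximum number of RBC units transfused over an 8-week period during the 16 weeks prior to Study Entry". In SAP 5.1 it is again the "maximum number of RBC units transfused over an 8-week period during the 16 weeks prior to Study Entry".

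Protocol 9.2.2 defines the same route as a "reduction of at least 4 units of RBC transfusions/8 weeks compared with the 8 weeks prior to start of treatment". The IWG 2006 table in protocol Attachment 6 also measures the fall "compared with the pretreatment transfusion number in the previous 8 weeks". The protocol uses the 16-week maximum to define the stratification factor (protocol 5.1), not HI-E.

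SAP 3.6 records the closure of the talacotuzumab arm and its consequence: "All analyses and summaries described in this document will include data only in subjects who received daratumumab". It says nothing about HI-E, and no other section explains the new comparator.

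**The concern.** The SAP replaces the protocol's comparator with one that is almost always equal or higher, and keeps the IWG 2006 label. Eligibility selects on the same quantity: "Received at least 4 units of RBCs over any 8 consecutive weeks during the 16 weeks prior to randomization". A subject enters because of a bad stretch, and that stretch then becomes the yardstick. Part of any later fall is regression to the mean, and a single-arm analysis has nothing to subtract it with.

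The stakes are limited. HI-E is a secondary endpoint, summarised as a proportion with a 95% Clopper-Pearson interval (SAP 6.2.2) and without a decision threshold. It gains weight if 6 or 7 of 30 subjects reach TI, because SAP 3.4 then gives secondary endpoints a larger part in the decision.

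**Working it through.** **Plan figures.** Neither document gives an expected HI-E rate, so there is none to reproduce. The zone where HI-E gains weight does reproduce: equal-tailed 80% intervals from Beta(0.5+m, 30.5−m) are (12.2, 30.6) for m = 6 and (14.8, 34.3) for m = 7, as in protocol Table 7 and SAP Table 1.

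**Direction.** Let M be the largest 8-week total in the prior 16 weeks, L the total in the last 8 weeks, and S the on-study 8-week total.
- SAP responder: M − S ≥ 4.
- Protocol responder: L − S ≥ 4.
- L is one of the windows over which M is taken, so M ≥ L. Every protocol responder is then a SAP responder.
- The extra SAP responders are those with L < S + 4 ≤ M.

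Example: M = 8, L = 5, S = 4. SAP: 8 − 4 = 4, responder. Protocol: 5 − 4 = 1, non-responder.

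The one exception is timing. M ends at randomization or study entry and L at first dose, up to 72 hours later (protocol 6.1). In simulations with a 3-day gap, L exceeded M in 1-6% of subjects, at most 0.9% responded in the first 8 weeks under the protocol comparator only, and the ends of the ranges below moved by less than 1 point.

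**Size with no drug effect (assumed inputs).** The documents give no within-subject transfusion variability. Assumptions:
- Gamma-distributed intervals between transfusions, with the same rate before and after entry.
- 1 or 2 units per transfusion; mean 4, 6 or 8 units per 8 weeks; interval CV 0.2, 0.33, 0.5, 0.7 or 1.0. That is 2 × 3 × 5 = 30 scenarios.
- 112 pre-study days and 182 follow-up days; entry requires M ≥ 4; 40,000 eligible subjects per scenario.

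Seven scenarios with simulated TI of 11.2-63.5% were dropped, because the higher supportive-care TI rate in the documents is 7.5% (SAP 3.3; protocol 11.2 gives 2.5%). In the 23 kept, M exceeds L in 60-79% of subjects, by 0.8-2.8 units on average. Transfusion-route HI-E with no effect:

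| On-study window | SAP comparator | Protocol comparator | Added by comparator |
|---|---|---|---|
| Weeks 1-8 | 0-49% | 0-23% | 0-25 points |
| Best of three 8-week blocks | 0-74% | 0-42% | 0-35 points |
| Any rolling 56 days in 6 months | 0-88% | 0-60% | 0-53 points |

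Repeat runs move these ends by a point or two. Across all 30 scenarios the pairs are 0-54% against 0-29%, 0-79% against 0-50%, and 0-90% against 0-66%. The addition is near zero for very regular 1-unit use. Of 30 subjects, 0-25 points is 0 to 0.25 × 30 = 7.5.

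A Poisson model (same means and unit sizes, between-subject CV 0 or 0.4, no TI screen) represents irregular transfusion. It adds 18-25 points in Weeks 1-8 (30-55% against 12-30%) and 24-36 points for the best 8 weeks in 24 (69-89% against 34-65%).

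**Hemoglobin route.** Compared with protocol 9.2.2, SAP 6.2.1 requires the rise to last at least 8 weeks (stricter), drops the condition that it be measured 28 days or more after a transfusion (looser), and averages pretreatment values (either direction).

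**The case against.** **The maximum has a rationale.** Eligibility makes M at least 4, so under the SAP every 8-week TI responder also meets the transfusion route of HI-E. The protocol comparator breaks that link. With M = 4, L = 3 and S = 0, the SAP fall is 4 and the protocol fall is 3, so a primary-endpoint responder fails transfusion-route HI-E. This stands as a real cost of the fix. The SAP does not give it as a reason, and if it was the intent it should be declared.

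**The SAP may supply detail.** Protocol section 11 defers specifics to the SAP, SAP 3.6 concerns study conduct, and protocol 9.2.2 already calls its criterion an adaptation of IWG 2006. So the absence from 3.6 is not evidence of concealment. But replacing a comparator that the protocol states is more than added detail.

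**SAP 3.1 words the burden differently**, as units in the 8 weeks before randomization. That text concerns stratification and conflicts with SAP 3.5, 5.1 and 6.2.1. It does not override the explicit definition in the same section as HI-E.

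**The sizes are not estimates.** This stands. The ranges include zero and rest on constant rates and complete follow-up. The TI screen discriminates little: 17 of the 23 kept scenarios have TI below 0.5%. The largest figures need a rolling best window, which the HI-E text does not specify.

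**A reader might infer that the SAP biases total HI-E upward.** The documents do not support that. HI-E is met by either route, and the SAP changes the hemoglobin route in both directions.

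**Conclusion.** The mismatch holds on the text, and the direction holds by arithmetic for the transfusion route with the other HI-E rules fixed, apart from the short gap before first dose. The net shift in total HI-E cannot be signed. The size is unknown: 0-25 added points in Weeks 1-8 is the range over assumed patterns with no drug effect, larger with a best-window rule and near zero for very regular 1-unit transfusion. The simulations do not apply Attachment 6's rule on pretreatment hemoglobin for counting transfusions.

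It would also be wrong to infer that the primary result is affected: TI counts transfusion-free days and uses no pre-study comparator. This is a correction that should be made to a descriptive secondary endpoint, mainly because that endpoint may be read closely if TI is inconclusive.

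**What to change.** In SAP 6.2.1:
1. Make RBC units in the 56 days before first dose the main comparator for transfusion-route HI-E, as in protocol 9.2.2.
2. State one on-study 8-week window for HI-E and apply it to both versions. Protocol 9.2.1 speaks of consecutive 8-week periods; the SAP's definition of transfusion amount allows any consecutive 56 days. A best-window rule yields some no-effect responders under either comparator.
3. Report HI-E against the 16-week maximum as a labelled sensitivity analysis.
4. Tabulate any TI responders who fail transfusion-route HI-E because they had fewer than 4 units in the last 8 weeks.

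If the sponsor wants the maximum so that every TI responder is also HI-E, the alternative is to declare and justify the departure from the protocol and report the protocol version alongside.

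The cost is SAP wording and programming. Transfusions in the 16 weeks before randomization are already recorded (protocol 8.1), and those after consent are recorded as concomitant therapy (protocol 8.2). The downside is a lower transfusion-route rate, and subjects with fewer than 4 units in the last 8 weeks cannot qualify by that route. They are 0-33% of simulated eligible subjects in the 23 kept scenarios and 0-35% in all 30.
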